8.2.5.2 OL-300 Analyses

The summaries described in Section 8.2.5.1 for the OL-500 period will be repeated for the OL-300 period using the worst intensity per symptom, subject and visit. The respective listings will present all intensities recorded.

8.2.6 Quality of Life Assessments

8.2.6.1 Food Allergy Quality of Life Questionnaires (FAQLQ)

8.2.6.1.1 General

This document is confidential

Statistical Analysis Plan

FAQLQs will be completed by study subjects 8 years old and older (FAQLQ-Child Form (FAQLQ-CF) for age range 8 to 12 years old, FAQLQ-Teenager Form (FAQLQ-TF) for age range 13 to 17 years old). Subjects who are 7 years old at the time of Visit 1 may also complete the form FAQLQ-CF at Screening (Visit 1), if their parent(s)/guardians(s) consider they are able to complete these questionnaires, so that when they turn 8 years old at Month 12, they will have a baseline questionnaire available. However, this is not mandatory.

Parents will also complete a FAQLQ questionnaire for subjects 0 to 12 years old (FAQLQ-Parent Form (FAQLQ-PF)) and for subjects 13 to 17 years old (FAQLQ-Parent Form Teenagers (FAQLQ-PFT)).

The FAQLQ forms will be completed at baseline, Months 12, 24, 36 or 48 and every 6 months during the Viaskin Milk open-label 300 μ g. The same questionnaire will be completed throughout the study according to the subject's age at Visit 1.

For the specific questionnaires the following sub-scores as defined in the respective scoring sheets - also available on www.faqlq.com - will be derived:

FAQLQ-CF (8-12 yrs) will be analyzed according to the 4 following domains [3]:

- EI: Emotional impact (Q no: 19-24),
- AA: Allergen avoidance (Q no: 4, 6-10, 15),
- RAE: Risk of accidental exposure (Q no: 11, 13-14, 16-17),
- DR: Dietary restrictions (Q no: 1-3, 5, 12, 18).

FAQLQ-PF (0-12 yrs) will be analyzed according to the 3 following domains [4]:

- EI: Emotional impact (Q no: 2, 6-7, 9-11, 23-28, 30),
- FA: Food-related anxiety (Q no: 1, 4-5, 16-17, 20-21, 29),
- SDL: Social and dietary limitations (Q no: 3, 8, 12-15, 18-19, 22).

The scores are calculated taking the reduced numbers of items for younger children into account: For children between 0-3 years old questions numbers 15 and higher are not applicable and for children aged between 4 and 6 years questions 27 to 30 are not applicable. Age at Visit 1 will be used to define which questions will be applicable during the study for each patient. Questions not needed will be not used for analysis.

These sub-scores rely on different numbers of items according to these age-groups (0-3, 4-6 and 7-12 years old).

FAQLQ-TF (13-17 yrs) will be analyzed according to the 3 following domains [5]:

- EI: Emotional impact (Q no: 5, 12, 19-23),
- RAE: Risk of accidental exposure Q no: 11, 13-15, 17-18),
- AADR: Allergen avoidance and dietary restrictions (Q no: 1-10, 16).

This document is confidential

Statistical Analysis Plan

FAQLQ-PTF (13-17 yrs) will be analyzed according to the 4 following domains:

- EI: Emotional impact (Q no: 20-27),
- FA: Food anxiety (Q no: 8-13),
- SR: Social restrictions (Q no: 14-19).
- DR: Dietary restrictions (Q no: 1-7).

For FAQLQ-CF, -TF and PTF total scores will be derived using the completed question directly. The total score from FAQLQ-PF will be calculated as mean of the 3 subscores - without adjusting for age-group.

The scores range from 1 (no problem/impairment) to 7 (maximal problem/impairment). A negative score in the changes to baseline means improvement.

The following instructions from the reference website (www.faqlq.com) will be used for the derivations of (sub-) scales:

- 1) Each question of the FAQLQ is answered on a 7-point scale (0 to 6) and should be recoded 1 to 7
- 2) The total FAQLQ-scores (except for FAQLQ-PF) and all sub-scores are calculated by dividing the sum of completed items by the number of completed items
- 3) If > 20% of items in any (sub-) scale are missing then the respective (sub-) scale is set to missing

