14.3.2 Food Allergy Quality of Life Questionnaire-Teenager Form (FAQLQ-TF)

FAQLQ-TF

Food Allergy Quality of Life Questionnaire – Teenager Form (13-17 years)

To cite this questionnaire:

The following questions concern the influence your food allergy has on your quality of life.

Answer every question by marking the appropriate box with an 'x'. You may choose from one of the following answers.

0	1	2	3	4	5	6
not	barely	slightly	moderately	quite	very	extremely

How troublesome do you find it, because of your food allergy, that you ...		0	1	2	3	4	5	6
1	must always be alert as to what you are eating?							
2	are able to eat fewer products?							
3	are limited as to the products you can buy?							
4	must read labels?							
5	have the feeling that you have less control of what you eat when eating out?							
6	are less able to spontaneously accept an invitation to stay for a meal?							
7	are less able to taste or try various products when eating out?							
8	must check yourself whether you can eat something when eating out?							
9	hesitate eating a product when you have doubts about it?							
10	must refuse treats at school or work?							
11	must be careful about touching certain foods?							
12	must carry an epinephrine auto injector CCI [REDACTED] ? (If you don't have an epinephrine auto injector mark an 'x' here 							

0	1	2	3	4	5	6
not	barely	slightly	moderately	quite	very	extremely

How troublesome is it, because of your food allergy, ...	0	1	2	3	4	5	6
13 that the ingredients of a food change?							
14 that the label states: "May contain (traces of)...."?							
15 that the labeling of the bulk packaging (for example box or bag) is different than the individual packages?							

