16 that you have to explain to people around you that you have a food allergy?							
17 that during social activities others can eat the food to which you are allergic?							
18 that during social activities your food allergy is not taken into account enough?							

How frightened are you because of your food allergy ...	0	1	2	3	4	5	6
19 of an allergic reaction?							
20 of accidentally eating the wrong food?							
21 to eat something you have never eaten before?							

Answer the following questions:	0	1	2	3	4	5	6
22 How discouraged do you feel during an allergic reaction?							
23 How disappointed are you when people don't take your food allergy into account?							

Food Allergy Independent Measure – Teenager Form (13-17 years)

The following four questions are about the chance that you think you have of something happening to you because of your food allergy. Choose one of the answers. This is followed by two more questions about your food allergy. Answer every question by putting an 'x' in the box next to the proper answer.

0	1	2	3	4	5	6
never (0% chance)	very small chance	small chance	fair chance	great chance	very great chance	always (100% chance)

How great do you think the chance is that you ...		0	1	2	3	4	5	6
1	will accidentally eat something to which you are allergic?							
2	will have a severe reaction if you accidentally eat something to which you are allergic?							
3	will die if you accidentally eat something to which you are allergic?							
4	can not effectively deal with an allergic reaction should you accidentally eat something to which you are allergic?							

5. How many products must you avoid because of your food allergy?	6. How great is the impact of your food allergy on your social life?

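### FAQLQ-TF item 5 is listed in both the Emotional Impact and AADR domains (24 assignments for 23 items), so one of the two item lists is very likely wrong

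*SAP*

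**What the plan says.** SAP section 8.2.6.1.1 defines three domains for the FAQLQ-TF:

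- First list, seven items: "EI: Emotional impact (Q no: 5, 12, 19-23"
- Second list, six items: "RAE: Risk of accidental exposure Q no: 11, 13-15, 17-18"
- Third list, eleven items: "AADR: Allergen avoidance and dietary restrictions (Q no: 1-10, 16"

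The range 1-10 in the third list includes item 5, which the first list also names. The SAP presents the domains as "the following sub-scores as defined in the respective scoring sheets" and points to the questionnaire's website for those sheets. They are not reproduced in the SAP or the protocol.

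On scoring, the section states that "all sub-scores are calculated by dividing the sum of completed items by the number of completed items", after recoding each answer from 0-6 to 1-7. It adds: "If > 20% of items in any (sub-) scale are missing then the respective (sub-) scale is set to missing". The TF total score is taken straight from the questions and not from the domains.

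The form is printed in Protocol appendix 14.3.2. Item 5 is one question, asking whether the teenager must "have the feeling that you have less control of what you eat when eating out". The last item is "23 How disappointed are you when people", so the form has 23 items.

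**The concern.** Nothing in the SAP says that an item may belong to two domains, and the rest of the same section treats domains as exclusive. In the child form, for example, item 5 is cut out of the allergen-avoidance list (4, 6-10, 15) and placed under dietary restrictions (1-3, 5, 12, 18). In the TF itself, the risk-of-exposure list steps around items 12 and 16, which are placed elsewhere. The unbroken range 1-10 is the only one that runs over an item already assigned. That looks like a slip: either 5 should have been left out of the range, or it should not be in Emotional Impact.

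Change in quality of life at Month 12 is a secondary endpoint (SAP 4.2.1). SAP 8.2.6.1.2 analyses each sub-score by ANCOVA, with adjusted differences from placebo, 95% confidence intervals and p-values. The same sub-scores are then summarised descriptively for the OL-500 period and, under SAP 8.2.6.1.3, for OL-300. An item in the wrong domain would carry into all of these.

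**Working it through.** **Step 1. Count the assignments.** The domain lists come from SAP 8.2.6.1.1 and the form lengths from Protocol appendices 14.3.1 to 14.3.4.

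| Form | Items on form | Items per domain | Assignments | Duplicated | Omitted |
|---|---|---|---|---|---|
| Child (CF) | 24 | 6 + 7 + 5 + 6 | 24 | none | none |
| Parent, 0-12 years (PF) | 30 | 13 + 8 + 9 | 30 | none | none |
| Teenager (TF) | 23 | 7 + 6 + 11 | 24 | item 5 | none |
| Parent, teenager (PTF in the SAP, PFT in the protocol) | 27 | 8 + 6 + 6 + 7 | 27 | none | none |

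Taking item 5 out of either list restores the count. If it is kept only in Emotional Impact, the sum is 7 + 6 + 10 = 23. If it is kept only in AADR, the sum is 6 + 6 + 11 = 23. The count alone does not say which is right.

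**Step 2. Effect on a sub-score.** Suppose a domain as listed has *k* items including item 5, and all are completed. The mean with item 5 minus the mean without it is

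(x5 − mean of the other k − 1 items) / k.

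- Emotional Impact, k = 7: 1/7 = 0.14 per point of difference, at most 6/7 = 0.86.
- AADR, k = 11: 1/11 = 0.09 per point of difference, at most 6/11 = 0.55.

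The factor 6 is the widest possible gap on a 1-7 scale. The shift is zero when item 5 equals the mean of the others.

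**Step 3. Effect on change from baseline.** The formula also applies to changes, with each score replaced by its change, when all items are complete at both visits. A gap that stays constant within a subject cancels. A mean difference between arms in change from baseline moves only if item 5 responds to treatment differently from the rest of its domain. It then moves by 1/7 or 1/11 of that differential response, before the ANCOVA's adjustment for baseline score. The documents give no data from which to estimate the differential response.

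**Step 4. Effect on the 20% missing rule.** The outcome changes only when item 5 itself is blank.

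- Emotional Impact, item 5 and one other item blank: 2/7 = 28.6%, set to missing. Without item 5 in the list: 1/6 = 16.7%, scored.
- AADR, item 5 and two other items blank: 3/11 = 27.3%, set to missing. Without item 5 in the list: 2/10 = 20.0%, scored, because the rule requires more than 20%.

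When item 5 is answered, both versions agree: one blank is tolerated for 6 or 7 items, and two for 10 or 11. A second blank in Emotional Impact is foreseeable, since item 12 concerns carrying an auto-injector and offers a separate box for teenagers who have none.

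**The case against.** The strongest objection is that the authority here is a scoring sheet which nobody can consult from the documents. The SAP nowhere states that domains must be exclusive, and a questionnaire can load one item on two scales by design. On that view there is an unexplained overlap but no demonstrated error. This stands as far as certainty goes: the documents cannot exclude a deliberate overlap or show which list is at fault. It does not remove the point, because three of the four forms in the section are exact partitions and no text allows an exception for the fourth.

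The literature citation does not help. SAP reference [5], cited for the TF domains, carries the title of the child-form validation paper, as reference [3] does. Protocol appendix 14.3.2 cites a different paper, on adolescents, for this form.

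Three stronger readings are tempting, and the documents do not support them:

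- A reader might infer that one TF sub-score is wrong at every visit. That requires the unseen sheet to make domains exclusive. Even then, a value changes only when item 5 differs from the mean of the other items or the missing rule gives a different result.
- A reader might infer that item 5 is counted twice in a score. It enters each sub-score mean once, and the total is built from the questions directly.
- A reader might infer that the shared item matters because it ties the two domains together. The plan summarises and models each sub-score separately and never combines or correlates the two.

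The SAP also describes the double-blind and OL-500 analyses as already run, and their programs may have followed the scoring sheet instead of the SAP text. The text alone does not show what was computed.

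**Conclusion.** The overlap is certain as printed, and a slip in one of the two TF lists is the best-supported explanation. That conclusion rests on the partition pattern of the other three forms and on the absence of any rule allowing an overlap.

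The reach is narrow. It covers subjects aged 13 to 17 at Visit 1, and either the Emotional Impact or the AADR sub-score. The uses affected are the Month 12 ANCOVA for that sub-score and the descriptive open-label summaries; the ANCOVA is not repeated after Month 12. The TF risk-of-exposure sub-score, the TF total, the other three forms and the primary endpoint are unaffected.

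The bounds of 0.86 and 0.55 points are limits for a single subject's score with all items answered. They are not estimates of a shift in a treatment comparison, which could be much smaller or nil. The item list is a stated scoring rule that very likely misallocates one item, so it should be corrected.

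**What to change.** 1. Check item 5 against the TF scoring sheet that the SAP names, and against the program that derived the TF sub-scores.
2. If the sheet gives item 5 to one domain, correct the SAP list: either AADR becomes 1-4, 6-10, 16, or Emotional Impact becomes 12, 19-23. If the overlap is intended, say so in the SAP.
3. Re-run the affected TF sub-score only for periods in which the program used the wrong list.
4. Correct reference [5] so that it points to the teenager-form source.

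The text change is one item list and one reference. The SAP still describes the OL-300 analyses as to come, so on that wording the correction can precede them at almost no cost. If the Month 12 program used a wrong list, the cost is a re-run of one TF sub-score's summaries and ANCOVA, and a correction to results already reported in the 12-month study report. If the program followed the sheet, only the SAP text changes.

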8.2.6.1.2 Double-blind Month 12 and OL-500 analyses

The total FAQLQ-scores and the respective sub-scores were summarized overall and for each type of questionnaire, in total and by randomized treatment group (placebo/dose level/overall active) at each time point using absolute value and change from baseline on the ITT for the randomized blinded treatment period.

Same analysis was performed overall and for each type of questionnaire, in total and by initial treatment group at each time point using absolute value and change from baseline on the OLS-500 for the Viaskin Milk 500 μ g open-label treatment period, if applicable. Similarly, the last value in the Viaskin Milk 500 μ g open-label treatment period was summarized.

Change from Month 12 was also tabulated at each time point of the Viaskin Milk 500 μ g open-label treatment period, if applicable.

The change from baseline (Visit 1) in QoL total scores and sub-scores at Month 12 was analyzed using an ANCOVA model for the randomized period. Treatment group and baseline score were included in the model. The adjusted LS-Mean differences versus placebo were reported together with associated 95% CI and p-values for each treatment contrast, i.e. for each pairwise comparison. These ANCOVA models will not be repeated for open-label time points.

This document is confidential

Statistical Analysis Plan

8.2.6.1.3 OL-300 Analyses

The following values will be summarized for the total FAQLQ-scores and the respective sub-scores using descriptive statistics overall and for each age group, visit and time point in total and by initial randomized treatment group (placebo/dose level/overall active) on the OLS-300.

- Absolute values at Month 0, Month 12, last value prior to switch to Viaskin Milk 300 μ g and all scheduled visits in the analyzed OL-300 period
- Changes from last value prior to any active treatment
- Changes from last value prior to switch to Viaskin Milk 300 μ g

8.2.6.2 Food Allergy Independent Measure (FAIM)

8.2.6.2.1 General

Each question of the FAIM is answered on a 7-point scale (0 to 6) and should be recoded 1 to 7. Total FAIM scores will be calculated by dividing the sum of completed items by the number of completed items. Total FAIM scores range from 1 “low perceived disease severity” to 7 “high perceived disease severity”. Calculation of total FAIM scores will be done only when 80% or more of the items are completed.

Some specific items mentioned below have to be reverse coded.

FAIM-CF: Child Form (8-12 years)

This questionnaire consists of 6 items. The mean score will be performed if at least 5 items are completed.

FAIM-PFC: Parent Form (Children aged 0-12 years)

There are 2 sections given in the questionnaire each with the same questions, one from the perspective of the parents (*What chance do you think your child has of.....?*) the other reflecting the thoughts of the child (*What chance does your child think he/she has of.....?*). Both mean scores of the parent's form (“Parent's thoughts” and “Child's thoughts”) are calculated as the mean of the single items, only if none of the items is missing. In both scores question 4 needs to be reverse scored.

FAIM-TF: Teenager Form (13-17 years)

This questionnaire is similar to the FAIM-CF and consists of 6 items. The mean score will be performed if a maximum of one item is missing.

FAIM-PFT: Parent Form (Adolescents aged 13-17)

The mean score “Teenager's thoughts” of the parent's form will be created similar to the total scores in FAIM-PFC as the mean of the single items. It will be calculated only if all items are available. Question 4 needs to be reverse scored.

8.2.6.2.2 Double-blind Month 12 and OL-500 analyses

This document is confidential

Statistical Analysis Plan

The total FAIM-scores were summarized overall and for each type of questionnaire, in total and by randomized treatment group (placebo/dose level/overall active) at each time point using absolute value and change from baseline until Month 12 on the ITT for the randomized blinded treatment period.

Same analysis was performed overall and for each type of questionnaire, in total and by initial treatment group at each time point using absolute value and change from baseline until Month 48 on the OLS-500 for the Viaskin Milk 500 μ g open-label treatment period, if applicable. Similarly, the last value in the Viaskin Milk 500 μ g open-label treatment period was summarized.

Change from Month 12 to each time point was also tabulated for the Viaskin Milk 500 μ g open-label treatment period, if applicable.

8.2.6.2.3 OL-300 Analyses

The following values will be summarized for the FAIM-scores using descriptive statistics overall and for each age group, visit and time point in total and by initial randomized treatment group (placebo/dose level/overall active) on the OLS-300.

- Absolute values at Month 0, Month 12, last value prior to switch to Viaskin Milk 300 μ g and all scheduled visits in the analyzed OL-300 period
- Changes from last value prior to any active treatment
- Changes from last value prior to switch to Viaskin Milk 300 μ g

9 SAFETY

The Safety Set was employed for all safety analyses on the randomized blinded treatment period and on the whole treatment or study period; OLS-500 was used for all safety analyses on the OL-500 period and OLS-300 will be used for the OL-300 period.

Safety analysis will generally be performed on the actual treatments given. In case of wrong dispensation, the subject will be analyzed according to the treatment received the longest.

9.1 EXTENT OF EXPOSURE

9.1.1 General

Extent of exposure was summarized using the exposure duration in the respective period, regardless of temporary interruptions, defined as:

Date of last patch application in the period - date of first patch application in the period + 1.

This document is confidential

Statistical Analysis Plan

Duration of patch application is assessed as recommended or not every day from Day 1 (Visit 4) up to Month 3 (Visit 9) on the subject diary cards. If duration of application is not as recommended, actual duration is recorded in hours and minutes per day. After Month 3 (Visit 9), application not as recommended were registered; actual duration is recorded in hours and minutes per day. Duration will be imputed with the recommended duration (6, 12 or 24 hours) for each day with duration assessed as 'as recommended'.

Reasons for patches not applied per protocol were classified a-posteriori in the randomized blinded treatment period (ITT) and the Viaskin Milk 500 μ g open-label period (OLS-500). The main reasons for patches not applied as per protocol, were subsequently pre-specified in the subjects' diaries as follows:

- Fell off
- Discomfort
- Personal convenience
- Investigator's decision
- Forgot
- Other

Inconsistencies in the data of diary cards are very common in clinical studies. In general the worst-case principle will be applied. Details of handling the different cases will be documented in a respective note-to-file document.

9.1.2 Double-blind Month 12 and OL-500 analyses

Exposure duration was summarized overall and for each age group, in total by initial treatment group (placebo/dose level/overall active) for the randomized blinded treatment period.

The above analysis was repeated overall and for each age group, in total and by initial treatment group, for the Viaskin Milk 500 μ g open-label treatment period as well as for the overall treatment period. Exposure duration in the Viaskin Milk 500 μ g open-label treatment period was summarized overall and for each age group, in total by initial treatment group using the following classes: [0-6] months, [6-12] months, [12-18] months, [18-24] months, [24-30] months, [30-36] months, [36-42] months, [42-48] months.

Mean daily exposure, defined as the total number of hours of application during a period divided by the number of days in that period, was summarized for the first 2 weeks of treatment, from the 3rd week to the Month 3 visit, from the Month 3 to the last patch application during the randomized blinded treatment period (Day 1 – Day 7, Day 8 – Day 14, Day 15 – Month 3, Month 3 - randomized blinded treatment end date).

The above analysis was repeated, overall and for each age group, in total and by initial treatment group for the Viaskin Milk 500 μ g open label treatment period, as well as for the overall treatment period.

This document is confidential

Statistical Analysis Plan

Number of days with patch not applied, defined as the total number of days with null daily duration of application, were summarized as a continuous variable overall and for each age group, in total and by actual treatment group (placebo/dose level/ overall active) for all subjects during the randomized blinded treatment period.

The above analysis was repeated, overall and for each age group, in total and by initial treatment group for the Viaskin Milk 500 μ g open label treatment period, as well as for the overall treatment period.

Reasons for patches not applied per protocol was summarized overall and for each age group, in total by initial treatment group (placebo/dose level/overall active) for the randomized blinded treatment period.

The above analysis was repeated, overall and for each age group, in total and by initial treatment group for the Viaskin Milk 500 μ g open label treatment period.

